The lavender essential oil used will be from the company doTERRA. This essential oil company was chosen because this company has a medical and science governing board made up of physicians, surgeons, chemists and pharmacists. The oil is also third party tested by [name] a trusted chemist in the essential oil community for purity and quality. Gas chromatography and mass spectrometry are used to ensure purity and no unwanted substances are in the essential oil. doTERRA's essential oils have also already been used in a hospital setting at Vanderbilt University hospital in Tennessee. doTERRA's essential oils were diffused in the Vanderbilt ER at the nursing stations. After 3 months of diffusing staff felt less work related stress, less time feeling overwhelmed, and had more energy at work [13].

5. Selection of Subjects:

Potential subjects will be selected from the clinic of [name]. Subjects will be consented by investigators or study key personnel.

Inclusion Criteria:

Women undergoing any form of breast reconstruction therapy Ages 18-85 At least a one night stay in hospital after surgery

Exclusion Criteria:

Sensitivity or allergy to coconut Use of sleeping aide drugs Use of benzodiazepines History of any of the following: asthma, eczema, allergy to flowers, smell disorders Sensitivity to lavender oil or any of its ingredients Pregnant women will be excluded from the study. During routine preoperative testing the patient's menstrual history or urine pregnancy test will be performed to identify any patient who is pregnant.

6. Subject Recruitment & Compensation:

Enrollment goal will be 60 subjects. We anticipate enrolling 60 subjects over 6 months and anticipate the trial to be complete within 1 year. The subjects will not be compensated for the study.

7. **Consent Process** – see Section 14 of the e-IRB submission form and complete the questions in that section.

8. Subject's Capacity to Give Legally Effective Consent:

9. Study Interventions:

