During surgery the patient will receive 4 drops of 50% solution lavender oil on the temple region over the temporal artery every 2 hours until completion of surgery. This will be applied by the anesthesia team. If the temporal region is not accessible the shoulders or feet will be alternate locations of application. When the patient arrives to the recovery room she will receive lavender oil through an oxygen mask. A 50 % solution will be used by placing 4 drops of the lavender solution on the mask and wiping it around the mask with a cotton ball. This delivery method will be used because this was used in a study from New York University Medical Center studying postoperative pain and no adverse events occurred [7]. When the patient is on the post-operative floor she will receive 50 % lavender oil on the wrist every 4 hours in the same manner as preoperatively from the hours of 6am to 9pm. Nightly (9pm-6am), 8 drops of 50% lavender oil will be placed on the cotton ball situated within 20cm of the patient. This method and concentration was chosen after reviewing a study in ischemic heart patients in the intensive care unit. The patients received lavender at bedside on a cotton ball and had statistically significant better sleep quality [6]. The control group will have coconut oil applied without any lavender oil applied in the same sequence as listed above. This will ensure the same procedures are carried out under both arms.

Blood pressure, pulse, respiratory rate, and oxygen saturation will be monitored in the preoperative area before lavender is given and 30 minutes after it is given. The level of pain will also be asked prior to application and at the second set of vitals. The control group will get two sets of vital measurements and pain scale measurements without any intervention. The same vitals will be recorded while the patient is under anesthesia every 30 minutes. There will be a notation in the chart when lavender is given to correlate time from application to time of vitals recorded. A review of the electronic medical record will be done to record amount of narcotic needed interop in both groups.

In the recovery room after the patient is given lavender through the oxygen mask the same vital signs and pain score measurement will be taken 15, 30, and 60 minutes from lavender application. In the control group on arrival to the recovery room the same data points will be

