measured with the same time intervals with coconut oil only. The amount of narcotic needed in the recovery room will be taken from the electronic medical record for each group.

Postoperatively on the floor vital signs as noted above will be recorded every 4 hours. At each 4 hour interval after the vital signs are taken lavender will be applied to the experimental group and no intervention in the control group. One more set of vitals signs will be recorded 45min after application of lavender each time lavender is applied. There will be a review of narcotic use from the electronic medical record from both groups. There will be a notation when lavender was given to correlate lavender application and narcotic use.

The anxiety questionnaire will be given preop before the application of lavender and then daily for every post-op day they stay. The questionnaire is called the hospital anxiety and depression scale.

The sleep questionnaire will be given in preop before application of lavender and then daily for every post-op day they stay. The sleep questionnaire is called the Richard Campbell Sleep Questionnaire.

Daily starting on postop day 1 the patient will also record their level of satisfaction of pain control from a scale of 1-10 with 1 being not satisfied and 10 being satisfied. Patients typically stay in hospital 1-3 days post-op. A survey will be filled out daily.

10. Risk/Benefit Assessment:

The use of lavender essential oil could have potential benefits to the patient:

- $\circ~$ Main benefits include decreased pain, better sleep, and better mood.
- o Other benefits include relaxation, calming environment, pleasing aroma.

Risks are minimal, but there is potential for some adverse events:

• Possible side effects include skin irritation or coughing.

- If skin irritation occurs, plain fractionated coconut oil will be applied to dilute the essential oil. Then a 4x4 cotton gauze will be used to wipe off the essential oil. The coconut oil will be applied a second time and then removed by a 4x4. Washing is not a recommend step because water will drive the essential oil into the skin further. If there is still a reaction and the patient is uncomfortable oral Benadryl will be given, 25mg PO Q6hrs prn itching or skin irritation. In the control arm, should the coconut oil irritate the skin it will be removed using a 4 x 4 cotton swab.

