- For coughing or any feeling of shortness of breath or chest discomfort, lavender oil therapy will be stopped. Any lavender applied to the skin will be diluted with fractionated coconut oil as mentioned above.
- For any serious, unexpected event, which occurs to any subject during this study the appropriate DUHS IRB Adverse Event notification will be completed, e-signed by the PI and submitted to the DUHS IRB within 5 days of notification of the reported event.
- Any patient who does not want to participate in the study can decline at any time.
- The patient's demographics including name will remain confidential.

11. Costs to the Subject:

Study intervention and Lavender Oil will be provided to subjects at no additional cost. Subjects and/or their regular insurance provider will be responsible for all procedures and tests considered standard of care for their condition.

12. Data Analysis & Statistical Considerations:

Study Design/Endpoints: The primary outcome will be a difference in pain scores between the 2 groups and/or decrease in narcotic use and/or increased patient satisfaction of pain control. Secondary outcomes are better sleep and decreased anxiety.

Analytic Plan and Method: Differences in the change scores of pain in the two groups as well any other demographic and clinical continuous variables will be examined using t-test or Wilcoxon test, depending on whether the variables are normally or non-normally distributed respectively. The differences between the categorical variables will be examined using chisquared or Fisher's exact test. Analysis will be conducted under the intention to treat (ITT). Missing data will be imputed under multiple imputation methods. Differences in the outcomes while controlling for potential covariates (age, etc) will be examined using linear regression. Significance of the tests will be assessed at alpha = 0.05. Analysis will be conducted using SAS 9.4 (SAS Institute, Inc., Cary, NC.).

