Power and Sample Size Calculations: A study called the effectiveness of lavender essence on sternotomy related pain intensity after coronary artery bypass grafting evaluated the effectiveness of lavender. The study observed pain scores of 6.45 (SD: 2.23) and 4.11 (2.13) in the control and treatment groups respectively [14]. For 80% power at alpha = 0.05, with the above observed means and standard deviations in the control and treatment groups, 15 subjects per group will be needed. Assuming about a 20% drop-out rate, the study would need 17 subjects per group.

13. Data & Safety Monitoring:

Data and safety monitoring will be reviewed by a team of experts (a least 2 physicians will be identified by the PI in this area of research and who are not associated with this study). Adverse events (AE) and serious adverse events (SAE) will be examined by the committee. We plan to have a review of the safety data in a meeting when half the study subjects are recruited into the study. The committee will decide on the continuity of the trial after reviewing the SAEs while ensuring the safety of the patients.

14. Privacy, Data Storage & Confidentiality – see Section 12 of the e-IRB submission form and complete the questions in that section.

References.

- 1. Jane Buckle. Clinical Aromatherapy Essential Oils in Healthcare. Churchill Livingstone Elsevier;2015.2-13.
- 2. N. Vakili and A. Gorji. Psychiatry and psychology in medieval Persia. *Journal of Clinical Psychiatry*. 2006;67:1862-1869.
- 3. A. Gorji and M.K.Ghadiri. History of headache in medieval Persian medicine. *Lancet Neurology*. 2002;1:510-515.
- 4. Aroma Tools. Modern essentials: a contemporary guide to the therapeutic use of essential oils. Utah: Aroma Tools; 2014. 11 p.
- 5. H. Woelk and S, Schlafke. A multi-center, double-blind, randomized study of the lavender oil preparation silexan in comparison to lorazepam for generalized anxiety disorder. *Phytomedicine*. 2010;17: 94-99.
- 6. Moeini M, Khadibi M, Bekharadi R, et al. Effects of aromatherapy on the quality of sleep in ischemic heart disease patients hospitalized in intensive care units of heart hospitals

of the Isfahan university of medical sciences. *Iranian Journal of Nursing and Midwifery Research*. 2010;15:234-239

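### Any one of three primary outcomes can carry the trial at an unadjusted 0.05, so a false primary claim is about 1.5 to 2.9 times as likely as with one endpoint

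*Combined protocol and SAP*

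**What the plan says.** All references are to the combined protocol and SAP.

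- **Section 12, Study Design/Endpoints.** The primary outcome is a "difference in pain scores between the 2 groups and/or decrease in narcotic use and/or increased patient satisfaction of pain control". Sleep and anxiety are secondary.
- **Section 12, Analytic Plan and Method.** Change scores of pain and other continuous variables "will be examined using t-test or Wilcoxon test, depending on whether the variables are normally or non-normally distributed respectively". In addition, "Differences in the outcomes while controlling for potential covariates (age, etc) will be examined using linear regression". On error control there is one sentence: "Significance of the tests will be assessed at alpha = 0.05".
- **Section 12, Power and Sample Size Calculations.** The calculation uses pain only: "For 80% power at alpha = 0.05, with the above observed means and standard deviations in the control and treatment groups".
- **Section 9, Study Interventions.** Pain is scored twice before surgery, and in the recovery room "pain score measurement will be taken 15, 30, and 60 minutes from lavender application". Narcotic use is taken from the record for the operation, the recovery room and the floor. For satisfaction, "Daily starting on postop day 1 the patient will also record their level of satisfaction of pain control", over a typical stay of one to three days.

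No section says which pain scores form the change score, which window defines narcotic use, or which day's satisfaction rating counts. No section gives a hierarchy, an alpha split, a composite or a multiplicity adjustment.

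**The concern.** Joining three outcomes by and/or lets any one of them satisfy the primary outcome. The 0.05 is then a level per test, and nothing holds the error rate for the primary claim as a whole at 5%. A null pain result with p = 0.04 on satisfaction would count as meeting the primary outcome.

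The pain outcome is not reduced to one test either. Several change scores can be formed, and both an unadjusted comparison and a covariate-adjusted regression with an open covariate list are planned, without saying which is decisive.

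Section 2 states that the goal is to support the use of lavender oil and complementary medicine in hospital. A positive primary claim would serve directly as that support, so its false-positive rate matters. The choice of endpoint also cannot be credibly made once results are known.

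**Working it through.** **1. The plan's own figure.** Inputs from the power paragraph: means 6.45 and 4.11, SDs 2.23 and 2.13, 80% power, alpha 0.05.

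- Difference = 6.45 − 4.11 = 2.34.
- Pooled SD = √[(2.23² + 2.13²)/2] = 2.181.
- Standardised effect = 2.34/2.181 = 1.073.
- A two-sample t-test at two-sided 0.05 needs 14.66, so 15 per group, as stated (power at 15 = 81.0%). A one-sided t-test would need 12.

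Sidedness is not stated, but the two-sided test reproduces the plan's number, so two-sided 0.05 is assumed below. The sizing treats pain as a single test at the full 0.05.

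**2. Chance of at least one qualifying false positive among the three.** The documents give no correlations between the outcomes, so a common correlation ρ from 0 to 0.8 is assumed, with each outcome oriented so that higher is better. Under no effect on any outcome, the three test statistics are taken as equicorrelated standard normal with critical value 1.96. Given a shared standard normal factor x, let

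- u(x) = Φ[(1.96 − √ρ·x)/√(1 − ρ)]
- l(x) = Φ[(−1.96 − √ρ·x)/√(1 − ρ)]

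An outcome that counts in either direction fails to qualify with probability u − l; one that counts only when favourable fails with probability u. The error rate is 1 minus the average over x of the product of the three terms.

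Three readings of the success rule:

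- (a) Literal wording: pain in either direction, narcotic use and satisfaction only if favourable. At ρ = 0: 1 − 0.95 × 0.975² = 0.0969.
- (b) Only results favouring lavender count. At ρ = 0: 1 − 0.975³ = 0.0731.
- (c) Either direction counts on all three. At ρ = 0: 1 − 0.95³ = 0.1426.

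| Reading | One endpoint | ρ = 0 | ρ = 0.3 | ρ = 0.5 | ρ = 0.8 | Multiple |
|---|---|---|---|---|---|---|
| (a) | 5% | 9.69% | 9.32% | 8.77% | 7.41% | 1.94 to 1.48 |
| (b) | 2.5% | 7.31% | 6.83% | 6.27% | 4.91% | 2.93 to 1.96 |
| (c) | 5% | 14.26% | 13.62% | 12.54% | 9.82% | 2.85 to 1.96 |

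Simulated t-tests with 30 per arm agree; at ρ = 0.5 they give 8.9%, 6.4% and 12.6% for (a), (b) and (c).

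**3. The open pain time point.** If any of the three recovery-room pain scores could serve as the pain result, there are five tests under reading (a). Simulation with 4 million draws gives 14.8% (assumed correlation 0.7 between pain scores, 0.3 otherwise) to 11.8% (0.9 and 0.5).

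**4. What control would cost.** Holm's first step for three endpoints is 0.05/3 = 0.0167. Two-sample t-test, effect 1.073, taking the SD of the change score equal to the cited SD of 2.181:

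| Completers per arm | Power at 0.05 | Power at 0.0167 |
|---|---|---|
| 19 | – | 78.3% |
| 20 | – | 80.8% |
| 24 (30 less 20%) | 95.3% | 88.6% |
| 30 | 98.3% | 95.1% |

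Power for narcotic use and satisfaction cannot be computed, because the plan gives no effect assumptions for them.

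**The case against.** - **The upper multiples do not come from the literal wording.** The text speaks of a decrease in narcotic use and an increase in satisfaction, so reading (a) is closest to it, and there the multiple is 1.5 to 1.9. This stands. The 2.9 belongs to reading (b), with (c) close behind at 2.85. At a correlation of 0.9, reading (a) falls to 6.7%, or 1.3 times. Correlation shrinks the excess; it does not remove it.
- **Pain is primary in practice.** The sample size rests on pain, and pain change scores are the only outcome named in the analysis sentence. That shows the likely intent, but the endpoint definition gives the other two outcomes equal standing, and nothing in the plan prevents a claim on either alone.
- **And/or may simply leave the success rule undefined.** The either/or reading is the natural one. If it is not intended, the plan states no success rule at all and the same repair is needed.
- **The analysis choice is less open than it looks.** The choice between t-test and Wilcoxon is tied to normality, so it is a loose rule and not two free tests, and an adjusted regression beside an unadjusted test is common practice. That is fair, and the analysis choice is not counted in the figures. The five-test figure depends on assumed correlations and on any recovery time being allowed to count.
- **The Holm power is conditional.** With equal SDs at both times, a change-score SD of 2.181 implies a pre/post correlation of 0.5. At 0.3 the SD is 2.58, and power at 0.0167 is 74% with 24 completers and 85% with 30; at 0 the SD is 3.08, and power is 56% and 68%. The 17 per group in the power paragraph would give only 72% even at 2.181, so the Holm route relies on the 30 per arm in Section 4. This bears on that route only.

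**Conclusion.** The concern holds. Followed as written, the plan lets the primary outcome be claimed on any one of three tests at 0.05, with no control over the three together. The chance of a false primary claim is 7.4% to 9.7% instead of 5% on the literal wording, and 1.5 to 2.9 times the single-endpoint rate across the three readings. These figures assume two-sided tests and a common correlation of 0 to 0.8. Freedom over the pain time point could raise the literal figure to about 12% to 15%, on the further correlations assumed.

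The power calculation for pain at 0.05 is not affected; the fault lies in the control of false claims. It should be corrected before analysis, because it decides what counts as success.

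**What to change.** The requirement is either one defined primary outcome or three with stated error control. Replace the and/or sentence in Section 12 with text such as:

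> Primary outcome: change in pain score from the preoperative pre-application score to 60 minutes after recovery-room application, compared by two-sample t-test at two-sided 0.05. Wilcoxon and covariate-adjusted regression are sensitivity analyses. Secondary outcomes, tested in this order at two-sided 0.05 only if every earlier test is significant: narcotic use over one stated window; satisfaction on postoperative day 1.

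The 60-minute score and the t-test are a proposal. The team may prefer another scheduled pain time or another planned analysis, but must fix one of each before analysis. Postoperative day 1 is suggested because it is the one satisfaction day that all patients share under the inclusion criterion "At least a one night stay in hospital after surgery".

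Alternatively, keep all three as primary, each as one defined variable with one analysis; define success as at least one significant result by Holm at an overall two-sided 0.05; and restate the pain power at 0.0167, giving the assumed SD of the change score.

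The cost is about four sentences: the outcome with its time point, the primary analysis, the testing order, and one definition each for narcotic use and satisfaction. The fixed order keeps pain at 0.05 and needs no extra patients. Holm needs 20 completers per arm for 80% power on the plan's pain effect, which 30 per arm covers if the change-score SD is near the cited one. The price is that narcotic use or satisfaction alone can no longer carry the trial at an unadjusted 0.05, and under the fixed order both become descriptive if pain is not significant.

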Research Summary

1. Protocol Title:

Effects of Lavender Oil on Postoperative Pain, Sleep Quality and Mood.

2. Purpose of the Study:

The purpose of this study is to evaluate the integration of lavender essential oil in surgical patients during the perioperative and postoperative phase of care. The study will assess patients' pain, sleep quality, and mood. The goal is to support that lavender oil will decrease pain scores and narcotic use, increase sleep quality, and decrease anxiety by improving overall patient satisfaction and supporting their natural sense of well-being. This research project will help support the use of complementary medicine in a hospital setting. The increased awareness and use of complementary medicine in a hospital setting will strengthen the patient centered care model that all hospitals strive to achieve.

3. Background & Significance:

Essential oils have been formally documented in use since the time of the Egyptians. The Ebers Papyrus document notes Egyptians using frankincense for different physical ailments [1]. In Greece Hippocrates used essential oils to fumigate the city of Athens to fight off the plague [1]. In medieval periods lavender essential oil was used for its antidepressive, anxiolytic, sedative, and analgesic properties. Medieval Persian physicians made records of their treatment plans which included lavender for depression and pain for headaches [2,3]. With the invention of steam distillation to separate the essential oil from the plant Europe began to use oils in perfumes and for medicinal benefits in the 1500's. Two physicians named Hieronymus and Brunschwig wrote one of the earliest printed books on the distillation and use of essential oils for medical benefits [4]. By the 19th century a French chemist Rene- Maurice Gattefosse was known for studying essential oils and their therapeutic benefits. His work and documentation led the way for the support of essential oil in medical ailments. Robert Tisserand in the early 1990s reviewed the French chemists work and added to his research to help make essential oils more known to the public in present day [1].

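### Mood is a stated study domain, but Section 12 pre-specifies only anxiety and names no score from the anxiety and depression scale

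*Combined protocol and SAP*

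**What the plan says.** All references are to the combined protocol and SAP.

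- **Section 1 (title):** "Effects of Lavender Oil on Postoperative Pain, Sleep Quality and Mood".
- **Section 2 (purpose):** "The study will assess patients' pain, sleep quality, and mood". The goal sentence that follows narrows this; its sleep and mood part reads "increase sleep quality, and decrease anxiety by improving overall patient satisfaction and supporting their natural sense of well-being".
- **Section 9 (interventions):** "The anxiety questionnaire will be given preop before the application of lavender and then daily for every post-op day they stay". The next sentence identifies it: "The questionnaire is called the hospital anxiety and depression scale". No score is named.
- **Section 10 (benefits):** "Main benefits include decreased pain, better sleep, and better mood".
- **Section 12 (endpoints):** "Secondary outcomes are better sleep and decreased anxiety". Neither depression nor a mood score appears as an outcome.
- **Section 12 (analysis):** change scores in pain, and other continuous clinical variables, are compared by t-test or Wilcoxon test. Linear regression is planned for covariate control, with age the only covariate named.

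**The concern.** The objective uses a broad term, the instrument covers two constructs by its own name, and the endpoint list names one of them. Two things follow. First, a report under this title would have a planned analysis for anxiety but none for any other aspect of mood, so a wider statement would rest on something chosen after the data were seen. Second, the anxiety outcome is itself not fully defined, because the plan does not say which score from the scale is meant.

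There is also an unused opportunity. The preoperative HADS is collected in both arms, but the analysis plan does not name it as a covariate for the postoperative comparison.

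**Working it through.** **1. Does any planned figure depend on this?** The only power calculation is for pain. Inputs from Section 12: means 6.45 and 4.11, SDs 2.23 and 2.13, 80% power, alpha 0.05 (two-sided assumed, since sidedness is not stated).

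- Pooled SD = sqrt((2.23² + 2.13²)/2) = 2.181
- Standardised difference = (6.45 − 4.11)/2.181 = 2.34/2.181 = 1.073
- Two-sided t-test solution = 14.66, rounded up to 15 per group

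The plan's 15 per group is reproduced. No HADS quantity enters it, so naming HADS outcomes changes nothing there.

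**2. Objective against endpoint.**

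| Domain in title and Section 2 | Section 2 goal | Measured in Section 9 | Outcome in Section 12 |
|---|---|---|---|
| Pain | lower pain scores, less narcotic | pain scores, narcotic use, satisfaction | primary |
| Sleep | better sleep quality | sleep questionnaire | secondary |
| Mood | less anxiety | HADS | secondary, anxiety only, score not named |

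Only in the last row does the term change between columns, and the instrument covers more than the listed outcome.

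**3. What a single HADS score could detect (orientation only).** A two-sided t-test at 0.05 with 80% power detects 0.74 SD with the planned 30 per arm. Applying the plan's 20% drop-out leaves 30 × 0.8 = 24 per arm, and 0.83 SD (0.826 unrounded).

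**4. What adjustment for the preoperative score would gain.** Assume equal variance before and after surgery, and correlation r between the two. Relative to an unadjusted comparison of postoperative scores (variance 1):

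- change score: 2(1 − r)
- regression on the preoperative score: 1 − r²

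Since 2(1 − r) − (1 − r²) = (1 − r)², which is never negative, adjustment is at least as precise as either alternative, apart from the one degree of freedom it uses. The documents give no r, so a range is assumed. The last column is 0.826 × sqrt(1 − r²).

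| Assumed r | Change score | Adjusted | Detectable at 24 per arm, adjusted |
|---|---|---|---|
| 0.3 | 1.40 | 0.91 | 0.79 SD |
| 0.5 | 1.00 | 0.75 | 0.72 SD |
| 0.7 | 0.60 | 0.51 | 0.59 SD |

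**5. What the extra comparison costs.** Counting one test per secondary outcome at 0.05, and treating tests as independent, the chance of at least one false positive is 1 − 0.95² = 0.0975 for two outcomes and 1 − 0.95³ = 0.1426 for three. Positive correlation between the two HADS scores would make the increase smaller.

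**The case against.** The best reply is that the protocol says what it means by mood. The Section 2 goal sentence expresses the mood aim as reduced anxiety, Section 9 labels the instrument an anxiety questionnaire, and Section 12 lists anxiety. Goal, label and endpoint agree, and a broad word in a title for a narrower construct is a labelling choice. Much of this stands. It shows that an anxiety outcome is consistent with the stated goal. It does not remove the broader wording in the title, the purpose sentence and Section 10, and it does not say which score is used.

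A second reply is that Section 12 tests other continuous clinical variables, which could include a depression score. That supplies a test, but does not make depression an outcome or fix its rank. Likewise, the open-ended covariate list could include the preoperative score, but does not commit to it.

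Three stronger readings are tempting and are not supported:

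- *The depression data go unused.* Nothing says they will be discarded, and the documents do not describe how the scale is divided. They show only that depression is not pre-specified as an outcome.
- *The trial cannot say anything about mood.* Anxiety is part of mood, and the full scale is collected in both arms.
- *A combined total would be used and would lose power.* No section proposes a total. Nor is the direction fixed. With equal SDs and between-part correlation rho, an effect on anxiety alone is multiplied by 1/sqrt(2(1 + rho)) on the total, but an equal effect on both parts by sqrt(2/(1 + rho)). For positive rho below 1, the first is below 1 and the second above it. The documents give no HADS SD, correlation or effect with which to choose.

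**Conclusion.** The mismatch is real and small. As written, the trial has a planned outcome for anxiety, with the score unnamed, and no pre-specified basis for a mood conclusion wider than anxiety. That part rests on the text alone and needs no assumption. It concerns secondary outcomes only.

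The precision gain from adjustment is certain in direction under the equal-variance model, but its size depends on an assumed correlation. It is slight at 0.3 and substantial at 0.7. No power loss can be attributed to the present wording.

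**What to change.** In Section 12:

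- Name the HADS anxiety score as the secondary anxiety outcome.
- Add the HADS depression score as a separate secondary outcome.
- Compare arms on each by linear regression adjusted for that score's own preoperative value, in place of the unadjusted t-test or Wilcoxon test.
- Name the postoperative day to which the comparison refers, since the scale is repeated daily and Section 9 gives a typical stay of 1 to 3 days.

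If the sponsor does not want a depression outcome, use anxiety in place of mood in the title, Section 2 and Section 10. The anxiety score and its adjusted analysis should still be stated.

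The cost is a short edit. It needs no new visits, questionnaires or patients, and the regression method is already in the plan. The downside is one more secondary comparison in a plan whose Section 12 states no multiplicity control, so the depression result should be reported as secondary whichever way it falls.
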